3.1.4. Duration of Treatment

Subjects in all cohorts may continue on treatment until disease progression, unacceptable toxicity, withdrawal of consent, death, or study termination, whichever occurs first.

3.1.5. Dose-Limiting Toxicity

The DLT-evaluation period is the first cycle of treatment. DLTs are graded according to the National Cancer Institute's Common Terminology Criteria for Adverse Events (NCI-CTCAE), version 4.03, and defined as any of the following events during the DLT-evaluation period:

- A delay of SEA-BCMA treatment by more than 7 days due to toxicity
- Any AE \geq Grade 3, unless deemed by the SMC to be clearly unrelated to SEA-BCMA (in Parts A through D) except for the following AEs, which must meet these specified criteria to be considered a DLT:
 - Grade 4 neutropenia lasting more than 5 days

- Thrombocytopenia \geq Grade 4, or Grade 3 thrombocytopenia with clinically significant bleeding
- Anemia \geq Grade 4 unrelated to underlying disease
- Any Grade ≥ 3 tumor lysis syndrome, including associated laboratory evaluations, that is not successfully managed clinically and that does not resolve within 7 days without end organ damage
- Any \geq Grade 4 IRRs or Grade 3 IRRs that do not resolve to \leq Grade 2 within 24 hours with infusion interruption, infusion rate reduction, and/or standard supportive measures. In the event of a Grade 3 IRR in $\geq 20\%$ of subjects (ie, 2 or more in the first 10 subjects), all subsequent subjects will require premedication and/or modification of infusion approach per the recommendation of the SMC. For subjects receiving premedication, any \geq Grade 3 IRR will be considered a DLT.
- Any Grade ≥ 3 asymptomatic laboratory abnormality that does not resolve, with or without intervention, to \leq Grade 1 or the baseline grade within 72 hours
- Any treatment-related death

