2. OBJECTIVES

This study will evaluate the safety and antitumor activity of SEA-BCMA as monotherapy and in combination in subjects with RRMM. Specific objectives and corresponding endpoints are detailed in [Table 1](#).

Table 1: Objectives and corresponding endpoints

Primary Objectives	Corresponding Primary Endpoint
Evaluate the safety and tolerability of SEA-BCMA monotherapy in subjects with relapsed or refractory multiple myeloma (RRMM) Identify the maximum tolerated dose (MTD) and/or optimal dose and schedule of SEA-BCMA monotherapy, and in combination with dexamethasone, in subjects with RRMM	Type, incidence, severity, seriousness, and relatedness of adverse events (AEs) Type, incidence, and severity of laboratory abnormalities Incidence of dose-limiting toxicities (DLTs)
Evaluate the safety and tolerability of SEA-BCMA in combination with SOC therapies in subjects with RRMM	
Secondary Objectives	Corresponding Secondary Endpoints
Identify a recommended single-agent dose and schedule of SEA-BCMA Assess the pharmacokinetics (PKs) of SEA-BCMA Assess the immunogenicity of SEA-BCMA Assess the antitumor activity of SEA-BCMA	Incidence of DLTs, cumulative safety and activity by dose level and schedule Maximum serum concentration and area under the serum concentration-time curve Incidence of SEA-BCMA antitherapeutic antibodies (ATA) Best response per the International Myeloma Working Group (IMWG) uniform response criteria (Kumar 2016) Objective response rate (ORR) Duration of objective response (OR) and complete response (CR) Progression-free survival (PFS) Overall survival (OS)
Exploratory Objectives	Corresponding Exploratory Endpoints
Assess incidence and level of BCMA expression in RRMM and relationship to clinical response to SEA-BCMA Assess the pharmacodynamic effects and biomarkers of response, toxicity, and resistance to SEA-BCMA Assess minimal residual disease (MRD) in subjects with very good partial response (VGPR) or better Assess impact of SEA-BCMA in combination with SOC therapies on health-related quality of life (HRQoL) from the subject's perspective.	Characterization of BCMA expression on malignant plasma cells Exploratory biomarkers of SEA-BCMA mediated pharmacodynamic effects Rate of MRD clearance Descriptive outcomes of qualitative interviews Maximum serum concentration and area under the serum concentration-time curve

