3.1.3.2. Part C: Dexamethasone Combination Therapy Cohorts

Enrollment into dexamethasone combination therapy cohorts may be initiated upon identification of tolerable SEA-BCMA monotherapy doses and schedules as determined by the SMC.

- In Cohort 1
 - SEA-BCMA will be administered at 1600 mg (the recommended monotherapy expansion dose) on Day 1 and Day 15 of each 28-day cycle (standard dosing).
 - Dexamethasone will be administered on Day 1, Day 8, Day 15, and Day 22 of each 28-day cycle.
- In Cohort 2
 - SEA-BCMA will be administered
 - at 800 mg (one dose level below the recommended monotherapy expansion dose) on Day 1, Day 8, Day 15, and Day 22 of Cycles 1 and 2 (intensive dosing), AND
 - at 1600 mg (the recommended monotherapy expansion dose) on Day 1 and Day 15 of Cycle 3 and subsequent cycles
 - Dexamethasone will be administered on Day 1, Day 8, Day 15, and Day 22 of each 28-day cycle.

In Cohort 2, a 3-subject cohort will be evaluated at dose level –1 ([Table 4](#)) initially. If 2 or more DLTs occur among the first 3 subjects, then Cohort 2 will be discontinued. If 1 DLT occurs among the first 3 subjects, the cohort will be expanded to 6 subjects, and only escalated if there are fewer than 2 DLTs among the 6 subjects. If 0 DLTs occur among the first 3 subjects, the dose will be escalated to 1600 mg q1wk for 2 cycles and then 1600 mg q2wk from Cycle 3 and beyond, the 6-subject safety run-in rules outlined below will be applied, and 3 additional subjects will be treated at 800 mg to complete the 6-subject safety run-in.

In Cohort 1 and Cohort 2, DLTs will be evaluated in the first 6 subjects enrolled at each dose level tested, in each combination therapy cohort.

1. If 0 or 1 of the first 6 subjects experience DLTs, the expansion cohort will proceed to enroll up to 20 subjects with the recommendation of the SMC.
2. If ≥ 2 DLTs occur in the first 6 subjects, MTD for the combination will be considered exceeded and the dose of SEA-BCMA will be de-escalated to the next lower dose level.
- If 0 or 1 of the first 6 total subjects at the lower dose level have experienced a DLT, the lower dose level will be declared MTD.

- If ≥ 2 DLTs occur in the first 6 total subjects at the lower dose level, MTD for the combination will be considered exceeded and the SMC will determine whether a further de-escalation will be tested, or if the combination cohort will be discontinued.

Subjects who are deemed not evaluable for DLT during dose finding will be replaced.

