3.1.3.3. Part D: Pomalidomide and Dexamethasone Combination Therapy Cohort

Enrollment into the pomalidomide/dexamethasone combination therapy cohort may be initiated upon identification of tolerable SEA-BCMA monotherapy doses and schedules as determined by the SMC. Part D will be conducted in the US only.

- In Cohort 1
 - SEA-BCMA will be administered at 1600 mg (the recommended monotherapy expansion dose) on Day 1 and Day 15 of each 28-day cycle (standard dosing).
 - Dexamethasone will be administered on Day 1, Day 8, Day 15, and Day 22 of each 28-day cycle.
 - Pomalidomide will be administered on Days 1 to 21 of each of each 28-day cycle.

DLTs will be evaluated in 6 subjects enrolled at the 1600 mg dose level. The dose will be considered tolerable if ≤ 1 DLT is observed among the first 6 subjects. Further expansion in Part D will be contingent upon review of the data from the 6 subjects in Cohort 1 and a protocol amendment.

Subjects who are deemed not evaluable for DLT during dose finding will be replaced.

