7.7.3.1. Relationship of the Adverse Event to Study Treatment

The relationship of each AE to each study treatment (SEA-BCMA, and/or dexamethasone, and/or pomalidomide) should be evaluated by the investigator using the following criteria:

Related:

There is evidence to suggest a causal relationship between the drug and the AE, such as:

- A single occurrence of an event that is uncommon and known to be strongly associated with drug exposure (eg, angioedema, hepatic injury, Stevens-Johnson Syndrome)
- One or more occurrences of an event that is not commonly associated with drug exposure, but is otherwise uncommon in the population exposed to the drug (eg, tendon rupture)

Unrelated:

Another cause of the AE is more plausible (eg, due to underlying disease or occurs commonly in the study population), or a temporal sequence cannot be established with the onset of the AE and administration of the study treatment, or a causal relationship is considered biologically implausible

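### In the Part C and D run-ins the general Grade ≥3 DLT criterion is keyed to SEA-BCMA alone, so ≤1 DLT in 6 can understate the toxicity of the combination it clears

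*Protocol*

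**What the plan says.** Protocol 3.1.5 gives one DLT definition for all four parts, assessed over Cycle 1. Its general criterion counts any adverse event of Grade 3 or higher "unless deemed by the SMC to be clearly unrelated to SEA-BCMA (in Parts A through D". No version is keyed to dexamethasone, to pomalidomide or to the regimen. Other criteria on the same list carry a different attribution test or none:

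- a SEA-BCMA delay of more than 7 days because of toxicity, with no drug named as the cause;
- "Any treatment-related death", with the treatment not specified;
- separate thresholds for neutropenia, thrombocytopenia, anemia, tumor lysis syndrome, infusion reactions and asymptomatic laboratory abnormalities.

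The count drives the run-ins. In Part C (Protocol 3.1.3.2): "If 0 or 1 of the first 6 subjects experience DLTs, the expansion cohort will proceed to enroll up to 20 subjects", subject to the SMC's recommendation; with two or more, "MTD for the combination will be considered exceeded". In Part D (Protocol 3.1.3.3): "The dose will be considered tolerable if ≤ 1 DLT is observed among the first 6 subjects". The matching primary objective in Protocol Section 2 is "Evaluate the safety and tolerability of SEA-BCMA in combination with SOC therapies in subjects with RRMM". Under Protocol 7.7.3.1 the investigator evaluates "The relationship of each AE to each study treatment", with the three drugs named separately.

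**The concern.** The objective and the conclusions concern a combination, while the general criterion concerns one component of it. A Grade 3 or 4 event on the tested regimen can drop out because it is put down to the partner drug. Compared with a count of toxicity from any study drug, the count used can only be equal or lower. It rests on separating two or three drugs given together, in six subjects per dose level, without a control. At stake are the expansion of a Part C dose level to as many as 20 subjects, the combination MTD, and the statement that the Part D dose is tolerable.

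The planned reporting does not let a reader recover the regimen-level figure. Incidence of DLTs is a primary endpoint in Table 1 of both documents. Yet Protocol 9.3.9.3 and SAP 6.6.2 report DLTs for dose escalation, and SAP 5.1 confines DLT summaries to that part. SAP 6.6.1 does list a summary of adverse events considered DLTs, but 5.1 restricts it, and it would in any case show only events already counted. The relatedness summaries in SAP 6.6.1 name SEA-BCMA only.

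**Working it through.** **Pass probability.** The documents give no operating characteristics for the run-in rule, so there is no stated figure to reproduce.

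Inputs:
- Rule: pass with 0 or 1 DLT among 6 subjects (Protocol 3.1.3.2 and 3.1.3.3).
- T, the proportion of subjects with a qualifying Cycle 1 event from any study drug: an assumption, varied from 25% to 50%. For scale, 25% is the Part A target DLT rate (Protocol 3.1.1.1); none is given for the run-ins.
- s, the share of those removed as clearly unrelated to SEA-BCMA: an assumption, varied from 0 to 75%.

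The counted rate is p = T × (1 − s), and P(pass) = (1 − p)^6 + 6p(1 − p)^5.

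At T = 40%:
- s = 0, p = 0.40: 0.0467 + 0.1866 = 0.233
- s = 25%, p = 0.30: 0.1176 + 0.3025 = 0.420
- s = 50%, p = 0.20: 0.2621 + 0.3932 = 0.655

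| T | s = 0 | s = 25% | s = 50% | s = 75% |
|---|---|---|---|---|
| 25% | 0.534 | 0.686 | 0.833 | 0.951 |
| 30% | 0.420 | 0.594 | 0.776 | 0.931 |
| 40% | 0.233 | 0.420 | 0.655 | 0.886 |
| 50% | 0.109 | 0.274 | 0.534 | 0.833 |

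**How far the delay criterion helps.** Protocol 5.2.3 turns a dose that cannot be given into an omitted dose: by the seventh day on the q2wk schedule, by the third day on the weekly one. Section 3.1.5 does not say whether an omitted dose is a delay of more than 7 days.

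If it is not, evaluability matters. Protocol 9.3.1.7.3 requires at least 75% of the intended Cycle 1 SEA-BCMA dose unless a DLT occurred. In Part D and Part C Cohort 1 there are two Cycle 1 doses of 1600 mg, so losing Day 15 leaves 1600/3200 = 50%. That subject would be non-evaluable and replaced, and so leave both numerator and denominator. On the weekly schedule one omitted dose leaves 3/4 = 75%, which still qualifies; two leave 50%, which does not. SAP 4.2 speaks of replacing q2wk patients who miss the second dose for reasons other than toxicity. This suggests that omissions for toxicity were meant to be handled differently, but the 75% requirement is kept.

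**The case against.** The case on the other side is substantial.

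- The bar is high. Only events clearly unrelated to SEA-BCMA drop out; doubtful, shared or interaction events still count.
- Other criteria can capture partner toxicity. The delay criterion names no drug, and Protocol Table 5 withholds SEA-BCMA for Grade 3 nonhematologic toxicity whatever its cause. Neutropenia and thrombocytopenia, the cytopenias in the pomalidomide table (Protocol Table 7), have their own thresholds. Anemia carries its own attribution wording, which suggests that the SEA-BCMA clause may not reach the listed events.
- The scope looks deliberate. The parts are named, the rule steers only the SEA-BCMA dose, and the partner drugs have set doses and their own modification tables.
- The count is not the only gate. Part C expansion needs the SMC's recommendation; Part D expansion needs data review and an amendment. The study-wide halting rules in Protocol 3.1.6.2 are not limited to SEA-BCMA. Adverse events and laboratory abnormalities are also primary endpoints.
- Counting every partner-drug event has a price. With no SEA-BCMA toxicity at all, a 20% rate of partner-only events would fail the run-in with probability 1 − 0.655 = 34%, and a 30% rate with 1 − 0.420 = 58%.

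Most of this stands as a limit on size, and the last item is a reason not to press one attribution rule. It does not remove the mismatch between count and objective. The study-wide halt is also a weak check on one small cohort. Pooled with the 65 planned monotherapy subjects (45 + 20), Grade 4 nonhematologic events in all six Part D subjects would be 6/71 = 8.5% if nobody else had one, against a threshold of 25%.

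A reader might infer that a partner-drug Grade ≥3 event is never a DLT, or that the run-in does not measure combination tolerability at all. The other criteria and the high bar rule out both readings. A reader might also infer that a fatal partner-drug event counts while a life-threatening one does not. The documents do not support that flatly. A life-threatening event may enter through the delay or listed-event criteria. Section 3.1.5 also does not define treatment-related: the any-drug reading is inferred from 7.7.3.1, while the cohort pause in 3.1.6.1 ties deaths to SEA-BCMA.

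**Conclusion.** The concern holds in a limited form: the run-in measures the tolerability of the combination incompletely, and any error is towards clearing the regimen. The size cannot be fixed from the documents. At an assumed 40% qualifying rate, excluding half of the events raises the pass probability from 23% to 66%, a factor of 2.8. At 25% with a quarter excluded, the change is from 53% to 69%; as the excluded share approaches zero, the effect disappears. These figures treat subjects as independent and assume that no other criterion captures the excluded events, so they lean towards the larger effect. The reporting gap needs no such assumption: DLT incidence is a primary endpoint for the combination, and the SAP plans no DLT summary for the run-ins.

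**What to change.** 1. Reconcile Protocol 3.1.5 with the combination objective and with the treatment-related-death criterion. State whether attribution is to SEA-BCMA or to any study drug, and whether the attribution clause reaches the separately listed events. Which rule applies is for the sponsor and SMC.

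2. Leave the decision rule as it is, but show the SMC, and report in the CSR for each Part C and Part D run-in, two counts of subjects with DLT-qualifying events:
   - those with events not clearly unrelated to SEA-BCMA;
   - those with events not clearly unrelated to at least one study drug.

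   Include subjects replaced as non-evaluable and identify them as such.

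3. Amend SAP 5.1 and 6.6.2 so that DLT summaries cover the run-ins as well as dose escalation.

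The cost is one extra table row per run-in. Investigator causality is already recorded for each drug; the SMC would record its view on the partner drugs at the same review. The downside is a second, possibly less favourable figure beside the DLT count, which will need explaining.

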3.1.6. Stopping Criteria

3.1.6.1. Enrollment Pause at the Cohort Level

If a subject's death is considered by the investigator, in consultation with the SMC, to be related to SEA-BCMA, enrollment will be paused within the applicable cohort until:

1. The case is reviewed by the investigator, the SMC, and the sponsor, and
2. The sponsor has notified applicable regulatory authorities of the outcome of the safety assessment and justification for restarting enrollment in the affected cohorts, and has received approval to resume, if required by local regulations.

3.1.6.2. Enrollment Halt for the Entire Study

Enrollment in the entire study will be halted by the sponsor if the overall benefit-risk balance is considered unfavorable.

The study will be halted if any of the following occur:

- Rate of on-study toxic deaths unrelated to underlying disease occurring within 30 days of dose exceeds 10% (initially, 2 or more out of up to 20 subjects; then 3 or more out of up to 30 subjects; 4 or more out of up to 40 subjects; etc.)
- Rate of Grade 4 nonhematologic toxicity unrelated to underlying disease exceeds 25% (initially, 5 or more out of up to 20 subjects; then 6 or more out of up to 24 subjects; then 7 or more out of up to 28 subjects; then 8 or more out of up to 32 subjects; then 9 or more out of up to 36 subjects; 10 or more out of up to 40 subjects; etc.)
- Rate of \geq Grade 4 allergic reactions that cannot be controlled with standard treatments exceeds 15% (initially, 3 or more out of up to 20 subjects; then 4 out of up to 26 subjects; then 5 or more out of up to 33 subjects; 6 or more out of up to 40 subjects; etc.)

Stopping criteria will be continuously monitored throughout the study by the sponsor in consultation with the SMC, considering enrollment halt if the incidence and/or the severity of toxicity leads to a risk-benefit assessment that is unacceptable to the study population. The sponsor will consult the SMC to consider whether to allow subjects already receiving treatment to continue, to consider modifying the protocol to continue the trial, or to terminate the study.

If enrollment is halted due to safety concerns, enrollment can only be restarted after appropriate amendments and notifications to Regulatory Authorities, with approval to resume, if required by local regulations.

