1.7.1. Risk Assessment

The nonclinical safety profile of SEA-BCMA has been evaluated in vitro and in vivo in the cynomolgus monkey model (Section [1.4](#)), in which no adverse effects were observed at the HNSTD. Monoclonal antibodies have the potential to cause infusion-related reactions (IRRs); a premedication plan for IRRs is described in Section [5.5](#), and study stopping criteria include a provision that the entire study will be halted if Grade 4 or higher allergic reactions that cannot be controlled with standard treatments exceed 15% at any point during the trial.

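### The study-halting rules say a rate must be exceeded, but 11 of the 13 listed counts halt at exactly that rate, and the lists stop at 40 of 131 planned subjects

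*Protocol*

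**What the plan says.** Protocol section 3.1.6.2 gives three criteria for halting the study. Each states a percentage and then, in brackets, the counts that put it into practice.

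- Toxic deaths: "Rate of on-study toxic deaths unrelated to underlying disease occurring within 30 days of dose exceeds 10" percent, with counts "initially, 2 or more out of up to 20 subjects; then 3 or more out of up to 30 subjects" and then "4 or more out of up to 40 subjects; etc".
- Grade 4 nonhematologic toxicity: "Rate of Grade 4 nonhematologic toxicity unrelated to underlying disease exceeds 25" percent, with counts "initially, 5 or more out of up to 20 subjects; then 6 or more out of up to 24 subjects", continuing through 7 in 28, 8 in 32, 9 in 36 and 10 in 40.
- Allergic reactions of Grade 4 or higher that standard treatment does not control: more than 15%, with counts 3 in 20, 4 in 26, 5 in 33 and 6 in 40.

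The same section says the criteria are monitored continuously. All three lists stop at 40 subjects and continue with an et cetera. Planned enrollment is up to about 131 (Protocol section 9.1). The benefit-risk text in section 1.7.1 repeats the allergic-reaction rule without counts, for reactions that "cannot be controlled with standard treatments exceed 15% at any point during the trial". The SAP contains no halting rule.

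**The concern.** The percentage and the counts should be two statements of one boundary. Read as written, they are two boundaries. The percentage requires the observed rate to be above the threshold, while most of the counts act as soon as the rate reaches it. The protocol handles this distinction correctly elsewhere: in section 3.1.5 the infusion-reaction trigger is written as at or above 20% and glossed as 2 in the first 10, which is exactly 20%.

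The rule is mandatory and covers the whole study. After a safety halt, enrollment restarts only after amendments and notifications to regulatory authorities. At a disputed boundary the sponsor, the safety monitoring committee and an inspector could each cite the same bullet for opposite answers. Past 40 subjects no count is listed, so whoever applies the rule must derive one, and the derived number depends on whether the words or the pattern of counts is followed.

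**Working it through.** **Inputs.** Thresholds t = 10%, 25% and 15%, the 13 listed pairs (r events, up to n subjects) and the starting counts m = 2, 5 and 3, all from Protocol section 3.1.6.2. Planned enrollment of 131 is from section 9.1. The true event rates below are assumptions; the documents give none.

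**Step 1: reproduce the listed counts.** Compare r/n with t.

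| Rule | Listed r/n | Result |
|---|---|---|
| Deaths, 10% | 2/20, 3/30, 4/40 | all exactly 10% (3 of 3) |
| Grade 4, 25% | 5/20, 6/24, 7/28, 8/32, 9/36, 10/40 | all exactly 25% (6 of 6) |
| Allergic, 15% | 3/20, 6/40 | exactly 15% (2 of 4) |
| Allergic, 15% | 4/26, 5/33 | 15.4% and 15.2%, above the rate |

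In total 3 + 6 + 2 = 11 of 13 equal the rate and 2 exceed it.

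**Step 2: which rule generates the list?** For a given r, the largest n at which the rate is at or above t is r/t rounded down: 2/0.10 = 20, 6/0.25 = 24, 4/0.15 = 26.7 giving 26, 5/0.15 = 33.3 giving 33. This reproduces all 13 upper limits. Requiring r/n strictly above t gives upper limits of 19, 29, 39 (10%), 19, 23, 27, 31, 35, 39 (25%) and 19, 26, 33, 39 (15%). Only 26 and 33 match. The counts therefore implement reaching the rate.

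**Step 3: where the two versions differ.** Holding the starting counts fixed, define for each n

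- listed pattern: c(n) = the larger of m and t × n rounded up;
- strictly exceeds: c(n) = the larger of m and (t × n rounded down) + 1.

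These differ only when t × n is a whole number that is at least m. For deaths, 2 in 19 (10.5%) halts under both versions; 2 in 20 halts under one. Over n = 1 to 131 they differ at 12 values of n for deaths (20, 30, ..., 130), 28 for Grade 4 (20, 24, ..., 128) and 6 for allergic reactions (20, 40, ..., 120). Subtracting the disputed sizes that are listed, 12 − 3 = 9, 28 − 6 = 22 and 6 − 2 = 4 lie beyond 40 subjects, where no count is printed. Example at n = 50: 0.10 × 50 = 5, so the listed pattern halts at 5 deaths (10%) and the wording at 6 (12%).

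**Step 4: effect on the probability of halting.** Let f_n(k) be the probability of k events in the first n subjects without a halt so far. Then f_n(k) = f_{n−1}(k)(1 − p) + f_{n−1}(k − 1)p for k < c(n), starting from f_0(0) = 1, and P(halt) = 1 − Σ f_131(k). Results, listed pattern versus strictly exceeds:

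| Rule | Assumed true rate | Listed | Strictly exceeds |
|---|---|---|---|
| Deaths | 3% | 0.14 | 0.13 |
| | 5% | 0.34 | 0.32 |
| | 10% | 0.85 | 0.84 |
| Grade 4 | 15% | 0.24 | 0.21 |
| | 20% | 0.56 | 0.52 |
| | 25% | 0.86 | 0.84 |
| Allergic | 5% | 0.09 | 0.08 |
| | 10% | 0.45 | 0.44 |
| | 15% | 0.85 | 0.85 |

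The differences are about 1 to 4 percentage points, and slightly less for allergic reactions at the ends of the range.

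A single look at n = 20 gives a misleadingly large contrast (for deaths at a true 10%, 0.608 with a limit of 2 against 0.323 with a limit of 3). The rule is monitored continuously, and most paths with 2 deaths by subject 20 already have 2 by subject 19, where both versions halt.

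**The case against.** The case for leaving the text alone is that the counts are explicit, can be applied as they stand up to 40 subjects, and are the more cautious version at every disputed point. On that view this is a wording slip with little operational effect. Most of this stands, and Step 4 supports it. It does not settle the rule beyond 40 subjects, where the counts must be derived, and it leaves section 1.7.1 repeating the percentage alone.

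Three stronger readings are tempting, and the documents do not support them.

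- A reader might infer that wording and counts conflict at every listed boundary. They agree at 4/26 and 5/33, and elsewhere they part only at the last n of a step.
- A reader might apply the percentage from the first subject, so that one death among the first 9 (11.1%) halts the study, and take the phrase in section 1.7.1 about any point in the trial as support. That would raise the death-rule halt probability at an assumed 5% to 0.47. But the bullets in section 3.1.6.2 qualify each percentage with a starting count of 2, 5 or 3 events, and section 1.7.1 is a one-line summary of those criteria. That stage has also passed: escalation is complete (section 3.1.1.2), with five levels, at least 2 evaluable subjects per level and 6 at 1600 mg, hence at least 4 × 2 + 6 = 14 subjects.
- A reader might say that no minimum number of events is stated. The starting counts supply it.

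**Conclusion.** The point holds as an internal inconsistency in a decision threshold. Section 3.1.6.2 words all three rules as exceeding a rate, 11 of its 13 counts equal that rate at the end of their step, and the unlisted range from 41 to 131 subjects can be filled in two ways. The practical size is small, about 1 to 4 percentage points in the probability of a halt.

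That size rests on assumptions: a constant true rate across all parts of the study, the listed pattern continued to 131 subjects, the same starting counts under both versions, and the assumed rates in the table. Step 1 needs none of them. A separate committee document, which the protocol mentions but which is not part of the protocol or SAP, might settle the question; these two documents do not. This is a minor correction and does not call the existence or general design of the stopping rules into question.

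**What to change.** Reconcile section 3.1.6.2 to one threshold per rule, either by changing the wording so that it matches the counts or by changing the counts so that they match the wording. Which threshold is right is a matter for the sponsor and the safety monitoring committee; no view is taken here.

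- If the wording changes to at or above, all 13 listed counts stand.
- If the wording stays, the upper limits become those for the strict version in Step 2.

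In either case, replace the et cetera with counts, or a formula, up to the planned 131 subjects, and supply the words meaning at-least that are missing from the 4-in-26 step. Make the allergic-reaction summary in section 1.7.1 refer to section 3.1.6.2 in the same terms. The cost is a word or two per bullet, or a revised list, and a short table. No new data or analysis is needed.
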